## **7. ADVERSE EVENTS AND REPORTING PROCEDURES**

### **7.1 Potential Adverse Events**

The adverse drug reactions in Phase 3 trials (i.e., events potentially associated with sarilumab administration) are upper respiratory tract infection, nasopharyngitis, oral herpes, urinary tract infection, neutropenia, leukopenia, thrombocytopenia, hypertriglyceridemia, injection site erythema, injection site rash, rash, urticaria, increased aspartate aminotransferase, and increased ALT.

Based on the preclinical and clinical studies of sarilumab as well as the safety profile of another IL-6 inhibitor (tocilizumab) and other biological DMARDs, hypersensitivity reactions, serious infections, and neutropenia, are an important identified risk with sarilumab administration. Important potential risks are thrombocytopenia and the potential risk of bleeding, clinically evident hepatic injury, an impact on CV outcome (MACE) secondary to LDL elevation, GI perforations, and malignancy.

### **7.2 Adverse Event Reporting**

All AEs regardless of seriousness or relationship to IMP/NIP, spanning from the signature of the informed consent form, until the end of the study as defined by the protocol for that patient, are to be recorded on the corresponding page(s) or screen(s) included in the CRF. Whenever possible, diagnosis or single syndrome should be reported instead of symptoms. The Investigator should specify the date of onset, intensity, action taken with respect to IMP, corrective treatment/therapy given, additional investigations performed, outcome and his/her opinion as to whether there is a reasonable possibility that the AE was caused by the IMP. Laboratory, vital signs or ECG abnormalities are to be recorded as AEs only if they are medically relevant: symptomatic or requiring either corrective treatment or consultation or leading to discontinuation or modification of

dosing and/or fulfilling a seriousness criterion and/or is defined as an AE with pre-specified monitoring.

### **7.2.1 Serious Adverse Events**

In the case of a serious adverse event the Investigator must immediately:

- ENTER (within 24 hours of knowledge) the information related to the SAE in the CRF and notify the DSMC.
- SEND a copy of all examinations carried out and the dates on which these examinations were performed, to Regeneron. Care should be taken to ensure that the patient's identity is protected and the patient's identifiers in the Clinical Trial are properly mentioned on any copy of source document. For laboratory results, include the laboratory normal ranges.
- All further data updates should be recorded in the CRF as appropriate, and further documentation as well as additional information (for Lab data, concomitant Medication, patient status) should be sent (by fax or e-mail) to the Monitoring Team within 24 hours of knowledge. In addition, any effort should be made to further document each Serious AE that is fatal or life threatening within the week (7 days) following initial notification.
- Following review by the DSMC, events meeting the IRB definition of 'Unanticipated Problem' will be reported to the IRB using eProtocol within 10 working days of DSMC review, or within 5 working days for deaths or life-threatening experiences.

## **8. CORRELATIVE/SPECIAL STUDIES**

### **8.1 Laboratory Correlative Studies**

Patient blood will be drawn in the Stanford phlebotomy lab and transported to the main clinical lab in the Stanford University Hospital for processing. The following blood and urine tests will be performed per the study calendar: chemistry panel, complete blood count with differential, erythrocyte sedimentation rate, C-reactive protein, angiotensin converting enzyme, quantitative immunoglobulins, 25-hydroxy vitamin D, serum pregnancy test, HIV-1/2 serology, hepatitis B serology, hepatitis C serology, quantiferon TB test, creatinine kinase, aldolase, lactate dehydrogenase, urine pregnancy test, urinalysis, urine protein/creatinine, and urine calcium. In addition, roughly 40 mL of research blood will be collected in heparin containing tubes and sent to the Stanford Clinical and Translational Research Unit (CTRU). Plasma and peripheral blood mononuclear cells (PBMCs) will be extracted. Plasma samples will be stored at -70 degrees for future study. PBMCs will be stored in liquid nitrogen for future study.

## 9. STUDY CALENDAR

	Screen Day -35 to 0	Baseline Day 1	Week 2	Week 4	Week 8	Week 12	Week 16	Week 18	Week 20	Week 24	Week 28	Week 34	ET	Unscheduled visit
Written IC	X													
Randomization		X												
Medical history	X													
Vital signs	X	X	X	X	X	X	X	X	X	X	X	X	X	X
Complete PE	X											X	X	
Limited PE		X	X	X	X	X	X	X	X	X	X			X
ePOST		X					X				X			X
Global VAS patient		X					X				X			X
Global VAS physician		X					X				X			X
FACIT-F and HAQ		X					X				X			X
Routine clinical labs:														
Chemistry panel	X	X	X	X	X	X	X	X	X	X	X	X	X	X
CBC w/diff	X	X	X	X	X	X	X	X	X	X	X	X	X	X
Urinalysis, urine P/C	X	X	X	X	X	X	X	X	X	X	X	X	X	X
ESR, CRP	X	X	X	X	X	X	X	X	X	X	X	X	X	X
Urine pregnancy		X	X	X	X	X	X	X	X	X	X	X	X	X
Sarcoidosis labs:														
ACE level	X	X					X				X			X
Immunoglobulins	X	X					X				X			X
Urine calcium	X	X					X				X			X
25-hydroxy vit D	X	X					X				X			X
Safety labs:														
Serum pregnancy	X													
HIV-1/2 serology	X													
Hepatitis B serology	X													
Hepatitis C serology	X													
QuantiFERON TB	X													
Screening tests:														
EKG	X													
Chest x-ray	X													
Sarcoid-specific tests:														
Pulm Function Test		X					X							
CT chest		X					X							
CK, aldolase, LDH		X					X							
Research labs:														
Plasma		X					X				X			
PBMCs		X					X				X			
Review AEs and meds	X	X	X	X	X	X	X	X	X	X	X	X	X	X
Study drug dispensing		X		X	X	X	X		X	X	X			
Drug accountability			X	X	X	X	X	X	X	X	X			X

## 10. MEASUREMENTS

### 10.1 Primary and Secondary Outcome measures

*Primary endpoint:* The primary endpoint is the flare-free survival of sarilumab-treated patients compared to placebo-treated controls in the double-blind randomized withdrawal period (Period 2) from Week 16 to Week 28. Patients will be considered to have flared if they receive rescue medication including increased glucocorticoids, or if they discontinue the study treatment in order to start a different therapy.

*Secondary endpoints:* The following secondary endpoints will all be assessed at Week 16 and Week 28 compared to baseline as a paired analysis: the change in the extrapulmonary physician organ severity tool (ePOST) score (17 organs rated 0-6, for a total score range of 0-102) [16], the change in global score of sarcoidosis using a visual analogue scale (VAS) by both the patient and physician (distance in mm measured on a 10 cm line), the change in FACIT-F score (fatigue scale ranging from 0-52 with higher score meaning less fatigue), the change in the Health Assessment Questionnaire (HAQ), the change in prednisone dose, the change in serum angiotensin converting enzyme (ACE), serum immunoglobulin G (IgG) levels, serum calcium, urine calcium, and serum 25-hydroxy vitamin D (25-OH-vit D), the change in pulmonary function tests (FVC, FEV1, and DLCO), the change in ALT, AST, and alkaline phosphatase, the change in serum creatinine and urine protein levels, the change in the Sarcoidosis Activity and Severity Index for cutaneous sarcoidosis (7 parameters scored 0-4 for a total score range of 0-28) [17], the change in CK, aldolase, and LDH, and the change in size of sarcoidosis lesions (i.e. enlarged lymph nodes, hepatic nodules, pulmonary nodules) by CT imaging. For patients with known or suspected ocular involvement, the secondary endpoint of change in ophthalmology global assessment of ocular sarcoidosis using a visual analogue scale (VAS) (distance in mm measured on a 10 cm line) [18] will be assessed, as well as the change in any one or more of the following parameters: best corrected visual acuity (BCVA), slit lamp examination (including grading of anterior chamber cells), tonometry, dilated indirect ophthalmoscopy (including grading of vitreous cells and haze), optical coherence tomography (OCT) and OCT angiography, color fundus photography, and fluorescein angiography.

From Week 16 to Week 28, time to flare will be compared between sarilumab-treated patients and placebo-treated controls as well as the proportion of patients in glucocorticoid-free remission at Week 28 between the two groups as additional secondary endpoints.

Safety will be assessed by counting and describing adverse events and abnormal laboratory results.

## 11. REGULATORY CONSIDERATIONS

### 11.1 Institutional Review of Protocol

The protocol, the proposed informed consent and all forms of participant information related to the study (e.g. advertisements used to recruit participants) will be reviewed and approved by the Stanford IRB. Any changes made to the protocol will be submitted as a modification and will be approved by the IRB prior to implementation. The Protocol Director will disseminate the protocol amendment information to all participating investigators.

## **11.2 Data and Safety Monitoring Plan**

We will form a Data and Safety Monitoring Committee (DSMC) consisting of two experienced rheumatology clinicians at Stanford University. The DSMC will audit study-related activities to determine whether the study has been conducted in accordance with the protocol, local standard operating procedures, FDA regulations, and Good Clinical Practice (GCP). This may include review of the following types of documents participating in the study: regulatory binders, case report forms, eligibility checklists, and source documents. In addition, the DSMC will regularly review serious adverse events and protocol deviations associated with the research to ensure the protection of human subjects. Results of the DSMC audit will be communicated to the IRB and the appropriate regulatory authorities at the time of continuing review, or in an expedited fashion, as needed.

## **11.3 Data Management Plan**

The Protocol Director and his team will prepare and maintain adequate and accurate participant case histories with observations and data pertinent to the study. Study specific Case Report Forms (CRFs) will document treatment outcomes for data analysis. Case report forms will be developed as paper forms and will be kept in a locked office, only accessible to the research team.

# **12. STATISTICAL CONSIDERATIONS**

## **12.1 Statistical Design**

Patient characteristics including demographics, medical history, and concomitant medications will be summarized. The summaries will be done using descriptive statistics, eg, mean, standard deviation, median, minimum and maximum for quantitative values and counts and percents for qualitative variables.

The primary efficacy analysis of flare-free survival in Period 2 from Week 16 to Week 28 will use the intention-to-treat (ITT) population and will be assessed with Kaplan-Meier methods. **Patients will be considered to have flared in Period 2 if they receive rescue medication including increased glucocorticoids, or if they discontinue the study treatment in order to start a different immunosuppressive therapy.**

For Period 1, secondary endpoint variables will be treated as continuous and the values at Week 16 will be compared to Baseline values using Wilcoxon signed-rank tests. The number of patients in glucocorticoid-free remission at week 16 will be reported. Patients will be considered non-responders in Period 1 if they are unable to complete the glucocorticoid taper, receive rescue medication including increased glucocorticoids, or discontinue the study treatment in order to start a different therapy. For Period 1 secondary efficacy endpoints, non-responders will be included in the analysis only if their prednisone dose is equal to or less than the starting dose and stable for the 4 weeks preceding Week 16. The rationale for this is that patients who flare despite sarilumab therapy might be given high doses of steroids, thus improving their endpoints and falsely attributing the success to sarilumab. As a sensitivity analysis, we will also assess the secondary outcomes using the baseline observation carried forward (BOCF) for those patients deemed non-responders.

For Period 2, time to first flare will be compared using a 2-sided log-rank test. The proportion of patients in glucocorticoid-free remission at week 28 in sarilumab-treated patients compared to placebo controls will be analyzed using a Fisher's exact test. The remaining secondary endpoint variables will be treated as continuous and the values at Week 28 will be compared to Week 16 and to Baseline values using Wilcoxon signed-rank tests. We will not perform any corrections for multiple hypothesis testing due to the exploratory nature of this pilot study which solely aims to generate areas of potential future investigation.

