### 1.2. Secondary Objectives

Secondary objectives of this study are to determine the number of patients in glucocorticoid-free remission and the change in prednisone dose compared to baseline at Week 16, after the open-label period (Period 1) of the study. Additional secondary objectives at both Week 16 and Week 28 are to demonstrate that sarilumab treatment is effective for reducing disease manifestation-specific metrics, for improving laboratory parameters, and for reducing cumulative prednisone dose. An important secondary objective is to demonstrate safety in this patient population.

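### The Period 1 rule for non-responders drops every patient whose prednisone dose has risen by Week 16 from the dose-change analysis, and BOCF scores each rise as zero

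*Combined protocol and SAP*

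**What the plan says.** Section 1.2 makes "the change in prednisone dose compared to baseline at Week 16" a secondary objective, and Section 10.1 lists "the change in prednisone dose" among the secondary endpoints.

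For Period 1, Section 12.1 plans that "the values at Week 16 will be compared to Baseline values using Wilcoxon signed-rank tests". It defines a non-responder as a patient who cannot finish the taper, is given rescue treatment (which includes more glucocorticoid), or stops study treatment to switch therapy. The Protocol Synopsis adds anyone who violates the taper schedule. A single inclusion rule then governs every efficacy endpoint that is secondary in Period 1. It reads: "non-responders will be included in the analysis only if their prednisone dose is equal to or less than the starting dose and stable". Stability is judged over the four weeks before Week 16. No endpoint is excepted.

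The reason given is that patients who flare may receive high steroid doses, "thus improving their endpoints and falsely attributing the success to sarilumab". The one sensitivity analysis is that "we will also assess the secondary outcomes using the baseline observation carried forward (BOCF) for those patients deemed non-responders". Separately, "The number of patients in glucocorticoid-free remission at week 16 will be reported".

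**The concern.** The rule suits endpoints that steroids can improve, such as ePOST, FACIT-F or ACE. For change in prednisone dose the logic reverses. Rescue steroids worsen this endpoint, so leaving out the patients who received them and ended above baseline favours the drug. Inclusion then depends on the outcome being measured.

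At stake is the size of the steroid reduction reported at Week 16. This is a named objective of a trial about freedom from glucocorticoids, and the planned estimate cannot show a dose increase in any patient.

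**Working it through.** **Step 1: follow a patient whose dose rose.** Suppose the Week 16 dose is above baseline.
- The patient has received increased glucocorticoid or departed from the taper, so is a non-responder (Section 12.1; Protocol Synopsis).
- The dose is above the starting dose, so the inclusion condition fails and the patient is left out of the main analysis. I take starting dose to mean baseline dose. If it meant the dose when the taper begins, which is no higher under the Synopsis, the condition would still fail.
- Under BOCF the Week 16 value is replaced by the baseline value, so the change is 0.

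Every change kept in the main analysis is therefore zero or a decrease, and no BOCF change can be positive.

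**Step 2: inputs.** Section 12.3 assumes that 80% of 15 patients respond: 15 × 0.80 = 12, which reproduces the plan's figure and leaves 3 non-responders. The documents give no baseline distribution and no rescue doses, so these are assumed: responder baselines evenly spaced from 10 to 40 mg (mean 25, sum 300) and all falling to 0; non-responder baselines of 15, 25 and 35 mg.

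**Step 3: all three non-responders rise.** Let S = 300 be the total responder reduction and R the total rise.
- Main analysis: -S/12 = -300/12 = -25.0 mg.
- BOCF: -S/15 = -300/15 = -20.0 mg.
- All 15 observed: (-S + R)/15.

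| Rises | R | Main | BOCF | All 15 observed | Gap, main | Gap, BOCF |
|---|---|---|---|---|---|---|
| 10 mg each | 30 | -25.0 | -20.0 | -270/15 = -18.0 | 7 | 2 |
| All raised to 60 mg (extreme) | 45 + 35 + 25 = 105 | -25.0 | -20.0 | -195/15 = -13.0 | 12 | 7 |

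Medians: -25.0 in the main analysis, and -20.9 both under BOCF and for all 15 observed. The gap is about 4 mg against the main analysis and none against BOCF.

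**Step 4: mixed non-responders** (a rise is +10 mg; a stable reduction is -10 mg and is kept by the rule).
- One rise, two reductions: main (-300 - 20)/14 = -22.9; BOCF -20.0; all 15 (-300 + 10 - 20)/15 = -20.7. BOCF errs slightly low.
- Two rises, one reduction: main (-300 - 10)/13 = -23.8; BOCF -20.0; all 15 (-300 + 20 - 10)/15 = -19.3.

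**Step 5: different assumed baselines.** With 12 responder baselines between 10 and 40 mg summing to 250 mg, and three patients rising: main -250/12 = -20.8; BOCF -250/15 = -16.7; all 15 observed from (-250 + 15)/15 = -15.7 (rises of 5 mg) to (-250 + 120)/15 = -8.7 (rises of 40 mg). The pattern is the same.

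**The case against.** The strongest reply is that little hangs on this. It is one of many secondary endpoints in an uncontrolled, open-label period of 15 patients, and Section 12.1 presents the study as an exploratory pilot. The Week 16 remission count is reported separately, so failures remain visible. By median, BOCF already gives the all-patient answer in the example. In means, BOCF is only 2 mg off when rises are 10 mg, and a 7 mg error needs all three non-responders at 60 mg. When some non-responders finish on a lower stable dose, BOCF can be slightly conservative.

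All of that stands and limits the size of the point. It does not remove it. The remission count shows how many patients failed, not how far their doses rose, and the exploratory label is used in Section 12.1 to justify uncorrected multiplicity, not this exclusion.

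Three stronger readings are tempting but unsupported:
- **That the rule manufactures significance.** Twelve decreases give an exact two-sided p of 2/2^12 = 0.0005 whatever happened to the others. Keeping all 15 gives 0.0013 with rises of 10 mg and 0.15 with all at 60 mg. But responders' doses fall largely because the taper is scheduled, so this p-value says little about drug effect either way. The point is the size of the reduction.
- **That the rule distorts cumulative prednisone in the same way.** Section 1.2 has an objective "for reducing cumulative prednisone dose", but Sections 10.1 and 12.1 define no such endpoint, and a cumulative dose has no baseline value to compare or carry forward.
- **That the main analysis could equally understate the reduction, because lower but unstable doses are also dropped.** The example does not show this. Even with all three non-responders at 0 mg, the all-patient mean is -(300 + 75)/15 = -25.0, equal to the main analysis.

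**Conclusion.** The concern holds for change in prednisone dose at Week 16. As written, neither planned analysis can register a rise, and the stated rationale does not fit this endpoint. When non-responders' doses rise, the main analysis overstates the mean reduction and BOCF corrects only part of it. With a 12/3 split, the assumed doses and all three rising, the overstatement in means is 7 to 12 mg for the main analysis and 2 to 7 mg for BOCF; the upper ends belong to the extreme case. Mixed non-responders shrink the gap.

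These sizes rest on assumed baselines and rises and on the plan's 80% response. The structural finding rests on the text alone. The Week 16 remission count and the Period 2 primary analysis are unaffected. This should be fixed before analysis, but it does not threaten the primary result.

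**What to change.** In Section 12.1, exempt change in prednisone dose from the exclusion rule and from BOCF, and keep both as written for the other endpoints. Then specify:
- **Headline analysis:** observed Week 16 minus baseline dose in all enrolled patients, including those who stopped sarilumab to switch therapy, with mean and median reported.
- **Sensitivity analysis 1:** the same, leaving out those who switched therapy, so that a reader can see how far their dose change affects the result.
- **Sensitivity analysis 2:** where the Week 16 dose is missing, use the last recorded diary or early-termination dose, and report the number missing by responder status.
- **Cumulative prednisone:** if a summary is reported under Section 1.2, compute it in all patients without the exclusion rule.

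The cost is a few lines of analysis wording and possibly a smaller reported reduction. The dose data are already planned: the Synopsis requires a daily steroid diary and attempted pill counts, and the Section 9 calendar marks medication review at every visit, including early termination and unscheduled visits. Some Week 16 doses may still be missing, because no section says that patients who leave keep the diary or attend Week 16. No treatment or dosing rule changes.

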## 2. BACKGROUND

### 2.1 Sarcoidosis

Sarcoidosis is a rare disease, but one that carries a high risk of morbidity and mortality with a 5 and 10-year mortality rate of 4 and 9% [1]. The prevalence is estimated at 10-20 per 100,000 of the general population, with roughly 50,000 people affected in the United States [2]. The incidence varies by region and ethnicity; the disease is roughly four times more common in blacks.

Sarcoidosis typically presents between the ages of 20 and 60 and a higher mortality exists in patients older than 55, non-Hispanic African Americans, and women [1]. The lungs are affected in the vast majority of patients (~90%), leading to fatigue, dyspnea, and often pulmonary fibrosis which can result in death. When the liver is affected, it can cause hepatic failure requiring transplantation. Ocular inflammation can permanently damage the eye, skin rashes are disfiguring, enlarged lymph nodes and glands can be painful, and inflammatory arthritis can be debilitating.

Sarcoidosis is often chronic, requiring long-term immunosuppression. There are no established guidelines for the treatment of sarcoidosis, but the mainstay therapy is glucocorticoids. It is well established that prolonged use of glucocorticoids has a number of harmful effects, including glucose intolerance, osteoporosis, weight gain, hypertension, hyperlipidemia, infection, insomnia, cataracts, gastrointestinal perforation, and mood changes [3-5]. Thus, it is essential for patients who do not respond to glucocorticoids to be treated with additional agents in hopes of minimizing exposure to steroids. Typically, a disease modifying anti-rheumatic drug (DMARD), such as methotrexate or azathioprine, is added to prednisone. When this fails, and for severe manifestations, more potent drugs are used such as cyclophosphamide or a biologic drug such as a TNF-inhibitor. Despite these therapies, many patients have ongoing sarcoidosis symptoms and organ injury.

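### The Period 1 filter on non-responders tests prednisone only, so a patient who moved to another drug can stay in the main Week 16 analysis and that drug's benefit be credited to sarilumab

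*Combined protocol and SAP*

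**What the plan says.** All the governing text is in one paragraph of Section 12.1.

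- **Who is a non-responder.** A patient who cannot complete the taper is a non-responder in Period 1, and so are patients who "receive rescue medication including increased glucocorticoids, or discontinue the study treatment in order to start a different therapy". Rescue medication includes increased glucocorticoids but is not limited to them.
- **Which non-responders are analysed.** In the secondary efficacy analyses, "non-responders will be included in the analysis only if their prednisone dose is equal to or less than the starting dose and stable", where stable means "stable for the 4 weeks preceding Week 16".
- **Why.** The stated reason: "patients who flare despite sarilumab therapy might be given high doses of steroids, thus improving their endpoints and falsely attributing the success to sarilumab".
- **The test.** Within the single open-label arm, "the values at Week 16 will be compared to Baseline values using Wilcoxon signed-rank tests".
- **Sensitivity analysis.** The plan will also "assess the secondary outcomes using the baseline observation carried forward (BOCF) for those patients deemed non-responders".

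Section 10.1 lists the endpoints concerned: ePOST, patient and physician VAS, FACIT-F, HAQ, prednisone dose, laboratory values, lung function, skin and eye measures, and CT lesion size.

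**The concern.** The definition of non-response has three routes, but the filter looks at one drug. It does not ask whether the patient is still taking sarilumab or has started something else. Section 2.1 makes a switch foreseeable in this population: when a conventional DMARD added to prednisone fails, "more potent drugs are used such as cyclophosphamide or a biologic drug such as a TNF-inhibitor".

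A switcher who improves on the new drug has less need for more steroid, so a prednisone filter may tend to keep exactly the patients whose Week 16 values say least about sarilumab. Period 1 has no control arm (Section 2.4), so nothing within it separates the effect of sarilumab from that of a replacement drug. The paired Week 16 tests are the plan's Period 1 evidence on disease metrics, and any contamination of this kind pushes them in sarilumab's favour.

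**Working it through.** **1. Reading the rule against a case.** Take a patient who begins the taper at Week 4, stops sarilumab partway through, starts another agent, and stays at the reduced prednisone dose already reached from Week 12 on.

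| Condition in Section 12.1 | This patient |
|---|---|
| Non-responder? | Yes: stopped to start a different therapy |
| Prednisone at or below starting dose? | Yes |
| Prednisone stable for 4 weeks before Week 16? | Yes |
| Still on sarilumab, no new drug? | Not asked |
| Result | Observed Week 16 value enters the main test, if it was collected |

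Nothing elsewhere closes the gap. Section 4.1 requires stable background DMARDs but attaches no analysis consequence. Section 4.2 does not remove a patient for switching.

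**2. How many patients the filter acts on.** Section 12.3 assumes 80% response among 15 patients: 15 × 0.80 = 12 responders, which reproduces the plan's figure, and 15 − 12 = 3 non-responders. With a binomial (15, 0.20) count of non-responders, P(at least 1) = 0.965, P(at least 2) = 0.833 and P(at least 3) = 0.602. How many of them would switch and pass the filter is not in the documents, so I take k = 0 to 3 as an assumed range. Their share of the analysed set is k/(12 + k): 7.7%, 14.3% and 20% for k = 1, 2, 3.

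**3. Effect on the test.** Assumptions: 12 responders whose changes are normal with mean 0 and SD 1 (no sarilumab effect); k switchers who improve by d = 1 to 2 SD; other non-responders filtered out; exact two-sided signed-rank test at 0.05; 400,000 simulated trials per setting. The spurious mean change is k × d/(12 + k).

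| k | Spurious mean change (SD) | Rejection, two-sided | Rejection in sarilumab's favour |
|---|---|---|---|
| 0 | 0 | 4.3% | 2.1% |
| 1 | 0.08 to 0.15 | 4.8% | 3.7 to 4.3% |
| 2 | 0.14 to 0.29 | 6.1 to 7.8% | 5.5 to 7.7% |
| 3 | 0.20 to 0.40 | 8.0 to 12.5% | 7.8 to 12.5% |

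The exact test is discrete. Its two-sided size with no switchers is 4.3%, 4.8%, 4.9% and 4.8% for 12, 13, 14 and 15 pairs, so the fair one-direction benchmark is 2.1 to 2.5%. One switcher leaves the two-sided rate where it was but shifts the rejections towards sarilumab.

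**4. Effect on the estimate.** Suppose sarilumab truly improves an endpoint by 0.5 SD and three switchers improve by 2 SD. Keeping their observed values gives a mean of (12 × 0.5 + 3 × 2)/15 = 0.80 SD. BOCF gives (12 × 0.5 + 3 × 0)/15 = 0.40 SD.

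**The case against.** - **A switcher does not automatically stay in.** The filter also requires four weeks of stable prednisone, and a failing patient may well need a steroid change while a new drug takes effect. Such a patient is excluded. This stands, and limits the point to those who pass.
- **The Week 16 value may not exist.** The plan does not say whether patients who stop sarilumab are followed to Week 16. The early-termination column of the study calendar (Section 9) has routine laboratory tests but no ePOST, VAS, FACIT-F, HAQ, sarcoidosis laboratory tests, lung function or CT. This also stands. However, the plan does not send switchers to that visit, and a filter defined on the weeks up to Week 16 presumes that some non-responders reach it.
- **BOCF is already planned.** It sets every non-responder to no change, so contamination would show as disagreement between the two analyses. But the main analysis would still be the contaminated one, and the plan does not say what to conclude if they differ.
- **These are uncorrected secondary tests in a pilot.** Section 12.1 calls the work exploratory. That lowers the stakes, but it does not explain guarding against one source of false attribution and not the other.

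A reader might infer that the Week 16 results will be biased, or that the trial's main conclusion is at risk. The documents support neither. The bias is zero if nobody switches. The remission count treats switchers as non-responders, and the Period 2 primary endpoint counts stopping study treatment to start a different immunosuppressive therapy as a flare.

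**Conclusion.** The gap is real and follows from the wording alone: applied exactly, the filter can admit patients treated with another drug to the main Week 16 secondary analyses, contrary to its own rationale. Its reach is limited to the Period 1 secondary efficacy endpoints.

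The size depends on an unknown number of switchers. With one, the two-sided error rate stays near 5%, although false findings in sarilumab's favour rise from about 2% to about 4%. With two or three, the effect is material. Three is the extreme of the range, because it needs every expected non-responder to have switched, passed the filter and supplied Week 16 data. The figures also rest on normal changes and an assumed 1 to 2 SD benefit from the replacement drug. The correction is worth making because it is cheap and best settled before Week 16 data are seen.

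**What to change.** In Section 12.1, state that in the main Period 1 secondary analysis any patient who started another immunosuppressive therapy or non-steroid rescue therapy before Week 16 is analysed by BOCF, not by the observed Week 16 value. Keep the prednisone filter for the other non-responders. Report how many patients the rule affects, and say whether Week 16 values are collected after sarilumab is stopped.

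Exclusion is not a good substitute, since dropping treatment failures can itself favour sarilumab. Nor is the last value before the switch: ePOST, VAS, FACIT-F, HAQ, lung function and CT are scheduled only at Baseline and Week 16 within Period 1, so without an unscheduled visit that value is the baseline one.

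One detail is needed for the clause to work. BOCF gives a change of exactly zero, and the usual signed-rank test discards zeros, so its p-value would equal that from exclusion. The plan should state how zeros are handled (Pratt's method ranks them before discarding) and report the median change over all patients in the analysis, BOCF patients included.

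The cost is a few sentences. A few observed values become no change, which is slightly conservative: in the example above, 0.40 SD instead of the true 0.50 SD with three such patients. Patient care is unchanged.
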